i) Take action in accordance with established VA regulations in case of adverse events, for example: he/she will seek immediate medical attention for the participant if necessary; if there is any doubt about the mental or physical status of a participant after testing he/she will consult with the available study physician. He/she will document and report all adverse events (e.g. skin lesion or significant skin discomfort) to the principal investigators. A study physician will evaluate the participant and make a recommendation for immediate or follow-up care if required. Telephone or in-person follow-up will be arranged as needed. Any participant judged on clinical grounds to have suffered adverse effects will thus be evaluated and treated as necessary and withdrawn from the study.

j) When not in use, assure the tDCS machine, electrodes, sponges, conductive gel, alcohol prep pads and normal saline are maintained in the secure location as assigned to [name] in Building 1 or 32, in a locked cabinet in a lockable room.

Management of Risks to Confidentiality:

This study will be conducted in compliance with Good Clinical Practice procedures. Strict standards of confidentiality will be maintained. Precautions will be taken to prevent disclosure of information to unauthorized parties.

All paper records, forms and data will be stored in secure files to which only members of the investigative team will have access. Computer records will be protected by standard measures that limit access of the data to designated trained research project personnel.

This research data will include participant information that may be of a sensitive nature. All patient data will be stored in locked files in lockable offices. Computers with subject data will be password protected and encrypted to ensure confidentiality of patient records. Specifically:

(1) Data sheets will be stored in one of the Principal Investigators' locked files in a locked office as assigned at the Providence VA Medical Center); (2) Data will be entered in coded form; (3) Data will be stored in computer files protected from unauthorized access by passwords; (4) Information that might potentially allow an individual participant to be identified will not be allowed in any publications, or reports sent to individuals outside the study; and (5) All

employees who are to handle data will be certified in Good Clinical Practice and Human Subjects Protection Training in confidentiality policies and procedures.

Adverse Event Reporting:

Throughout the study, participants will be monitored by the research assistant and research staff for adverse events. The research team will meet bimonthly and/or as needed to review the logistics of the study and review all adverse events and problems. The PI's will review all adverse events (AE) and serious adverse events (SAE) as soon as reported and will submit reports as required by the SOP's (Standard Operating Procedures) of the Providence VA.

Adverse events (AE) will be defined as any reaction or side effect that occurs during the course of the clinical trial. A new illness, symptom, unfavorable or unintended sign, or worsening of a pre-existing condition or abnormality will be considered an AE. Serious Adverse Events (SAEs) will be defined as any fatal event, any immediately life-threatening event, any permanent or substantially disabling event, and any event that requires or prolongs inpatient hospitalization. Any unexpected event that suggests a significant hazard, contraindication, side effect or precaution will also be reported. One of the PI's will promptly report all SAEs to the PVAMC IRB within twenty- four (24) hours by telephone, and follow with a completed SAE Form within two (2) days. The completed SAE Form will include demographic information, a narrative explanation of the event, and photocopies of any relevant source documents from the participant's case report forms. As a result of an AE or SAE the PI's will address whether there is a need to re-design or amend the protocol or a need to change the description of risk, either in the consent form or in the protocol

Medical Care for Research-Related Injuries

In the event of research-related injuries to participants in this project, medical care related to that injury will be provided at no cost to the participant.

Potential Benefits

This study is designed to measure the potential benefits of tDCS for treating pain. This is an investigational study and therefore we cannot guarantee that patients will indeed experience a reduction in symptoms of their chronic low back pain. Participating in this study, however, may serve to benefit advances in understanding chronic pain, potentially leading to future improvement in treatments.

Risk-Benefit Ratio

Furthering knowledge regarding the brain mechanisms underlying the affective component of the chronic pain experience may provide significant benefit in developing alternative effective treatments for chronic pain. The approach taken in this research may provide beneficial treatment for this debilitating condition. Additionally, transcranial direct current stimulation, or tDCS, is classified by the FDA as a minimal risk technique. Therefore, we believe that the potential benefits of this study greatly outweigh the potential risks that may occur as a result of participating in this study.

DATA COLLECTION AND SECURITY:

Excel, SPSS and Word will be used for data collection, licenses for this software is held by the VA. Participant data collected for this study will be stored and processed on passwordprotected VA desktop computers. Paper files will be stored in a lockable office in a PI's locked file at the PVAMC as assigned. The participants' demographics, screening questionnaires, consent forms and HIPAA authorizations will be stored, separate from study data files

All study data will be labeled only with the participants' unique study code, which will be assigned at random. Only the Principal Investigators and their designated research staff will have access to the unique code linking the research data to the participants' identifiers. This link will be stored separately at the PVAMC in a PI's lockable office in a locked file as assigned.

The study data will be stored on the Shared Research drive (P-drive) at the Providence VA Medical Center in the restricted folder: [\\ R04pronas21\research_protocols\ [name] \tDCSCLBP-R](#). No VA data will be removed from the PVAMC site.

Records will be maintained in accordance with the Department of Veterans Affairs Record Control Schedule 10-1. The PHI will be destroyed per the Department of Veterans Affairs Record Control Schedule 10-1.

The PI's ([name] and [name]) will be responsible for assuring that VA access accounts are terminated when a user no longer needs access. In the event that a theft, loss, or other unauthorized access of sensitive data or storage devices occurs, as well as non-compliance with security controls, the Information Security Officer (ISO) will be notified immediately. Research staff will carry out any necessary procedures given by the ISO in order to resolve the situation.

Data collected from this study will be used for research purposes. Information that might potentially allow an individual participant to be identified will not be allowed in any publications or reports or sent to individuals outside the study. Information that could potentially allow an individual participant to be identified will not be shared with any researchers who are not directly involved with the study.

DATA ANALYSIS

Data analysis will be conducted using standard statistical software, SPSS, the license is held by the Providence VA. Data will be analyzed through linear models including (M)ANOVA, repeated measures analyses and mixed linear model procedures to deal with correlational effects. This will be followed by appropriate post-hoc analyses comparing specific conditions. In order to maintain anonymity in restricted data files participants will be only listed with their unique identification code. Clinical rating scales will be scored as they are in clinical use. Word and Excel will also be used, PVAMC hold licenses for these programs.

There is no power analysis as this is an exploratory study.

STUDY LOGISTICS

Training of Research Personnel

Prior to initiation of the study all research personnel will be trained in the specifics of this research project according to their role. Research personnel responsible for administering

assessments and questionnaires will be trained by the PIs and Co-PIs. Ongoing training will occur as needed, especially if the study is amended and for review of the logistics and progress of this project.

All research staff will have completed research ethics training; including data management and procedures for maintaining data confidentiality and safety before being allowed to work on the project.

Urine pregnancy tests will be done through the VA laboratory according to their standard operating procedures.

Location of Study

Recruitment will occur at the Interventional Pain Clinic. The study assessments and treatment will be conducted at PVAMC, in one of the PI's areas as assigned in Building 1 or Building 32. Renovations to space in these areas are pending. Prior to the scheduled study visit participants will be clearly informed what building and office their study session will occur. Study staff contact information will be provided so participants may call with questions about the location.

FUNDING AND COMPENSATION

Material Inducements

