On the first day of treatment, prior to the tDCS treatment, females of childbearing age will be required to have a urine pregnancy test before any study procedures. The female participant will be brought to the PVAMC laboratory where the clinical laboratory staff will be handling and processing the participant's urine, do the pregnancy testing, and report the results as part of their daily clinical responsibilities. The pregnancy test will be done through the PVAMC laboratory according to their standard of practice. Research key personnel will not handle or have contact with the participant's urine for this pregnancy test. Participants are informed in the study consent form of this requirement to give permission for a pregnancy test to be involved in this study and

that the results will be recorded in their PVAMC medical record. Any participants that show a positive pregnancy test will be considered a screen failure.

Participants will be asked to complete the DVPRS, WHY-MPI, RMDQ, PHQ-9, GAD-7, PASS, CPAQ-8, CEQ, CSQ-8, and the Sleep Measure. This will provide a baseline measure in regards to the sensory/perceptual component of their pain, the degree to which pain interferes with daily activity, and the emotional component of their pain.

Prior to this and each study treatment, designated research staff will assess the skin on the participant's scalp where the electrodes will be placed to assure there are no lesions, cuts, or exclusionary skin disorders. Participants will be positioned for optimal comfort on a chair, recliner, or stretcher. Designated trained research staff will attach the electrodes to the participant's scalp (participants will not need to have any hair shaved) and apply the flexible rubber headband to keep them in place (see detail below). Participants will be educated that research staff will be monitoring them continuously through a non-recording closed-circuit camera from another room or he/she will be physically present in the room to assess if they need anything or want to stop the tDCS.

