The participant will then receive either the sham or active tDCS stimulation based on their random group assignment for twenty minutes (tDCS details are below). Following tDCS stimulation, only the DVPRS will be repeated. This measure will be used to determine whether immediate pain relief following stimulation occurs. Lastly, in order to monitor the effectiveness of the blind, participants will be asked to guess which treatment, active or sham, they received.

On subsequent treatment days, the DVPRS will be repeated before and after stimulation and the Sleep Measure will be repeated before stimulation.

At the end of the first week of treatment, session five, in addition to the DVPRS and the Sleep Measure, the WHY-MPI, RMDQ, PHQ-9, GAD-7, PASS, and CPAQ-8 will be repeated.

During the second week, the DVPRS will again be administered before and after each treatment, and the Sleep measure will be repeated before stimulation

On the final day of treatment, in addition to the DVPRS and the Sleep Measure, the WHYMPI, RMDQ, PHQ-9, GAD-7, CEQ, CSQ-8, PASS, and CPAQ-8 will be repeated.

Follow-up assessments will occur by phone approximately six (6) weeks after the last tDCS treatment session and will consist of the same measures as session ten.

tDCS details:

Equipment used for tDCS Intervention, the Neuroconn DC-STIMULATOR PLUS, is a micro-processor-controlled constant current source. tDCS is a non-invasive procedure in which a device sends a small Direct Current (DC) across the scalp to modulate brain function. A lowlevel current from the positive electrode, anode, is sent to the negative electrode, cathode. When the extremely low level current passes from the anode to the cathode, it may simultaneously increase the activity of the brain by the anode and decrease the activity of the brain near the cathode. The DC-stimulator meets the highest safety standards thanks to (hardware- and software-based) multistage monitoring of the current path. It continuously monitors electrode impedance and it can detect insufficient contact with the skin and automatically terminate stimulation to reliably prevent participant injury.

The FDA recognizes the tDCS device as a non-significant risk device. During each treatment session, tDCS will be applied to the scalp using a Neuroconn DC- Stimulator Plus (Figure 1).

Figure 1. tDCS device

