There are minimal risks to be incurred from participating in this study. Specific risks related to the clinical and cognitive assessments (study questionnaires) and tDCS are described below. Participants may be uncomfortable sitting or lying for an extended period of time on the chair, recliner or stretcher due to their CLBP.

Risks and discomforts due to Clinical and Cognitive Assessment Administration:

There are several questionnaires that the participant will be asked to answer. The time it takes to answer these questions may create frustration or fatigue. Answering the clinical symptom rating questions may involve sensitive information that could cause emotional reaction, embarrassment or discomfort. Previously undisclosed or unknown mental health problems may be identified.

Risks due to tDCS:

There is some inherent risk with tDCS. Mainly there is a risk of skin irritation where the electrodes are attached to the scalp, which in the literature has been mostly limited to transitory redness. No toxic effects have been found, and the procedure carries few risks (Brunoni, et al., 2012). At the levels we are proposing, only a few publications report minor injuries, and the stimulation is widely considered to be “safe” (Bikson, et al., 2009). In rare cases, when skin around stimulation sites was non-intact, or when the stimulation was delivered for a long time without proper conductive solutions being applied to the electrodes, a few minor burns and skin lesions have been observed (Frank, et al., 2010). If electrodes/sponges are placed over preexisting skin lesions, such as vascular moles and angiomas there may be a greater conductance than the surrounding skin, increasing the risk of irritation or possible burns. Care is thus taken to exclude potential participants who exhibit broken or marked skin near the sites of the electrodes. The electrodes in this study are soaked in normal saline. A study using the same amperage proposed in this protocol found no mood or cognitive changes due to tDCS (Iyer, et al., 2005). Transient, very rare post-tDCS effects have been found to include mild headaches, nausea, and insomnia (Poreisz, et al., 2007).

PROTECTION OF THE SUBJECT

Participants will be reminded that they may stop participating in the study at any time for any reason without affecting their VA health care or relationship with PVAMC.

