does not increase tissue temperature and the 4 x 1 configuration leads to a negligible increase in scalp temperature (Datta et al., 2009). In safety studies conducted at City College of New York (CCNY) and during usage at the National Institutes of Health (NIH), sets of these electrodes did not cause skin problems more serious than tingling and transient redness when applied to the skin of the arm with current densities up to 2.56 mA/cm² and durations of up to 22 minutes ([name], personal communication). It was also found that cathodal current produced the most skin irritation. However cathodal stimulation will be of crucial importance to our study design as we hypothesize that our target brain areas may be overactive, and hence require suppression. During cathodal stimulation we will take extra precautions that consist of instructing the participants to advise the research staff of any discomfort during testing, inspection of stimulation sites as needed and immediate discontinuing stimulation if discomfort occurs.

The tDCS device that will deliver the direct current is adjustable in both intensity as well as duration of stimulation. In addition, the device will be 9V battery-driven to function as a constant current stimulator with a maximum output in the milliamps range with absence of the risk of sudden large intensities of electrical current that could occur with an electrical driven device.

Prolonged passage of direct current across metallic electrode (where electrons from the stimulator are converted to ions carried through the body) can produce undesired electrochemical products such as pH changes. The sponge pocket will act to physically separate, and thus buffer, the skin from electrochemical changes. The normal saline used on the sponges assists in preventing burns. In addition, electrodes/sponges will not be placed over cuts, or skin lesions such as vascular moles and angiomas that might have greater conductance than the surrounding skin. One set of sponges will be used throughout the study for each participant. Electrodes will be held in place by using special head bands made of flexible rubber.

All participants will be carefully screened prior to tDCS for contraindications to tDCS (see exclusion criteria). At least one PI will be available on an immediate basis for all study treatment sessions.

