tDCS will be administered by the tDCS Operator - a trained and qualified individual supervised the principal investigators to deliver, or assist in delivery of, tDCS. Training includes the knowledge of safety considerations and precautions associated with tDCS.

The tDCS operator will:

- a) Assess the participants' scalp skin where the electrodes will be placed to assure it is intact,
free of lesions, cuts or exclusionary skin disorders.
- b) Prepare and position the electrodes and tDCS device on the participant for accurate brain stimulation according to the protocol prior to initiation of stimulation.
- c) Operate the hardware associated with the tDCS device to assure the level of current and amount of time is accurate per protocol.
- d) Administer the tDCS, at the parameters established by the tDCS Attending Physician as per identified in this protocol.
- e) Assess the participant's mental status and general clinical condition before and after tDCS

to assure the safety of the participant to have tDCS and the safety of the participant to return home.

f) Monitor the participant during the tDCS session to assess for potential occurrence of adverse events.

g) Make routine adjustments to the placement of the device as required and consistent with product labeling (e.g., to ensure contact between participant's head and electrode) during the tDCS session. The tDCS Operator may not independently make any revision to pre-determined stimulation dose or electrode position parameters prescribed by the study protocol.

h) Determine if tDCS should be interrupted or terminated (e.g., participants express increasing discomfort to their skin under the electrodes; participants show signs of discomfort or other stress; participant wants to discontinue study procedures).

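### Adverse-event monitoring is promised for the whole study, but the schedule has no structured adverse-event question and no routine skin check after stimulation, so late effects of session 10 may be under-recorded

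*Combined protocol and SAP*

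**What the plan says.** **Expected effects.** Risks due to tDCS states: "Mainly there is a risk of skin irritation where the electrodes are attached to the scalp". It also mentions rare minor burns and lesions. On symptoms it says: "Transient, very rare post-tDCS effects have been found to include mild headaches, nausea, and insomnia".

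**The commitment.** Adverse Event Reporting has the research assistant and research staff monitor participants for the whole study. It defines an adverse event as "any reaction or side effect that occurs during the course of the clinical trial". It gives no question, form or time point for finding one.

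**Procedures around sessions.**
- Study Visits: before each treatment, "designated research staff will assess the skin on the participant". Operator item a) repeats this check.
- Operator item e): mental status and general condition are assessed before and after tDCS.
- Operator item f): "Monitor the participant during the tDCS session to assess for potential occurrence of adverse events".
- Management of Risks due to tDCS: extra precautions during cathodal stimulation include "inspection of stimulation sites as needed and immediate discontinuing stimulation if discomfort occurs".
- Study Visits: after stimulation on day 1 the only questionnaire repeated is the DVPRS, and the participant guesses the assignment. On later days the DVPRS is given before and after stimulation and the Sleep Measure before it.
- Operator item i): adverse events are documented and reported, with telephone or in-person follow-up as needed.

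**After session 10.** The one scheduled contact is a phone call at about six weeks, which "will consist of the same measures as session ten". Those measures are pain, interference, disability, mood, anxiety, pain-related fear, acceptance, expectancy, satisfaction and sleep. Table 1 marks sleep at follow-up as an outcome.

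**The concern.** Effects described as arising after stimulation can begin once the participant has gone home. They are best found by asking at the next contact, and skin effects by looking. During the course there is always a next visit within a few days. After session 10 there is none, and the call six weeks later is defined by an outcome battery with no adverse-event content.

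Two things are at stake. The first is the participant: someone with an electrode-site lesion after the last session is identified only if it is noticed before they leave or if they report it. The protocol itself says that cathodal current irritated skin most, and cathodal stimulation is the planned intervention. The second is the evidence. For a pilot study, tolerability is a main output. A low count has little meaning if nobody was asked, and unprompted reporting may also differ between arms.

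**Working it through.** The documents state no figure to reproduce: there is no power analysis and no assumed side-effect rate. The check is a comparison of sections, followed by a count and an illustration.

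**Step 1. What would find each named effect?**

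| Effect | After sessions 1-9 | After session 10 |
|---|---|---|
| Skin irritation, burn, lesion | General-condition check after tDCS; inspection as needed; routine skin check before the next session | General-condition check after tDCS; inspection as needed; then spontaneous report. A phone call cannot inspect skin |
| Headache, nausea | General-condition checks after tDCS and before the next session; not asked by name | General-condition check after tDCS; then spontaneous report; not asked by name on the call |
| Insomnia | Sleep Measure before the next session | Sleep Measure on the call, about six weeks later |
| Other events | General monitoring, method not stated | General monitoring, method not stated |

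The right-hand column loses the backstop for skin, headache and nausea. For insomnia it keeps a question, but one asked about 42 days later. The Sleep Measure section describes that instrument as an in-office report covering the ten testing days, so its recall period on the call is unclear.

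**Step 2. How many sessions are affected?** Study Population gives 20 participants per arm and Research Plan gives 10 sessions each. If all complete:
- active sessions: 20 × 10 = 200;
- active final sessions: 20 × 1 = 20, which is 20/200 = 10%;
- sham final sessions: also 20, where few stimulation effects are expected but the same question is needed for comparison.

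**Step 3. What can 20 active participants show?** This is an illustration only; the rates and capture fractions are assumptions. Let p be the proportion of active participants with a late effect and c the fraction of those effects that are recorded. The chance of recording at least one is 1 − (1 − p·c)^20.

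| p | c = 1 | c = 0.5 | c = 0.25 |
|---|---|---|---|
| 1% | 18% | 10% | 5% |
| 5% | 64% | 40% | 22% |
| 10% | 88% | 64% | 40% |

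If no event is recorded among 20, the one-sided 95% upper limit for p·c is 1 − 0.05^(1/20) = 13.9%. With full capture that is also the limit for p. With c = 0.5 the limit for p is 13.9%/0.5 = 27.8%, and with c = 0.25 (unrounded 13.91%) it is 55.6%. A zero count from 20 people is weak evidence in any case, and much weaker when capture is incomplete or unknown.

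**The case against.** The case for leaving the plan alone has real content.

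- **Monitoring is promised for the whole study.** Adverse Event Reporting says so, and it refers to local operating procedures and case report forms that are not in the document. Staff may well ask on the call. A reader might infer that effects are watched for solely around the sessions. The documents do not support that; they support saying that the method after session 10 is not stated.
- **Session 10 is observed.** Operator item e) applies after every session, including the tenth, and covers safety to go home. Item i) names skin lesions and significant skin discomfort as events to report. This stands; what is lacking is a routine look at the skin at that point.
- **Sleep is asked about at six weeks.** A reader might infer that no named effect is asked about after session 10. That is wrong for insomnia, although a brief episode six weeks earlier could be missed.
- **The effects are called transient and very rare.** A reader might treat the six weeks to the call as unobserved time at risk and conclude that most of the trial is unmonitored. That does not follow: for transient effects the relevant period is shortly after session 10. Nor do the documents show that events will probably be missed, because spontaneous reports count.
- **The risk-benefit statement does not depend on these counts.** It rests on the FDA classification and expected knowledge, and Data Analysis plans no side-effect rate. Under-recording would not overturn either.
- **A skin checklist could unblind.** The staff who administer the outcome scales are blinded, and scalp effects may differ between arms. This is a valid constraint on the remedy.

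These points narrow the concern without removing it. The schedule, followed exactly, leaves the last session with no routine skin check after stimulation and no scheduled question on headache, nausea or skin, in either arm.

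**Conclusion.** The point holds in limited form. The general commitment to monitor adverse events is not carried into the schedule: no contact has a structured adverse-event question, and no routine skin check follows stimulation. Sessions 1-9 are partly covered by the next visit. Session 10 is not, so its late effects may be under-recorded.

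The gap concerns 20 active final sessions (10% of 200) if everyone completes. The number of missed events is unknown, because the documents give neither a rate nor a capture fraction, and it may be small. The conclusion assumes that the written schedule describes what staff will do; unseen procedures or forms could already supply the missing question. The efficacy comparison is not affected. This is a worthwhile, inexpensive improvement to participant safety and to the tolerability data, not a fault that undermines the trial.

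**What to change.** 1. **Checklist.** Add to Table 1 a short fixed side-effect checklist (scalp skin, headache, nausea, sleep, other). Use the same words in both arms. Give it before sessions 2-10 about the time since the last session, after session 10, and on the six-week call about the time since session 10.
2. **Blind.** Give it after the outcome questionnaires at that contact, or have it given by staff who do not rate outcomes, so that skin reports cannot influence the ratings.
3. **Skin look.** Have the tDCS operator record a look at both electrode sites when the sponges are removed at every session, including session 10. This is in addition to the existing "inspection of stimulation sites as needed" during stimulation and does not replace it.
4. **Text.** State in Adverse Event Reporting that these are the means by which events are elicited, so that the commitment and the schedule agree.

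**Cost.** One form and, as a working estimate, one to two minutes per contact. With nine pre-session contacts, one after session 10 and the call, that is 11 contacts, or 11 to 22 minutes per participant against the roughly 18 hours already planned. No visit is added and treatment is unchanged. More minor events will be recorded in both arms, and a small unblinding risk remains, which the ordering or staffing controls. The call still relies on recall over six weeks, so brief symptoms after session 10 may be lost. The change narrows the gap without closing it completely.
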